Block randomisation with variable block sizes will be used within each of two gestational age strata: $28^{+0}-33^{+6}$ weeks' gestation and $34^{+0}-36^{+6}$ weeks' gestation. These gestational age strata are chosen to reduce the possibility of a chance imbalance in gestational ages between the intervention and controls groups, post-randomisation, as the severity of RDS is inversely related to gestation. Infants of multiple births, of which more than one infant are eligible, will be randomised individually.

The order of the block sizes (4, 6, or 8) will be randomly selected and the assignment of will be random within each block, until the selection is forced. Random numbers will be generated by SAS 9.4 using randomly selected seed numbers; the seed will be selected by opening a large book and choosing left or right page by coin toss (heads=right).

Ramaiah hospitals will be provided with consecutively numbered, sealed opaque randomisation envelopes containing the assigned treatments: the two gestational strata will be differentiated using different colours. The envelope will be opened after written consent has been obtained and the infant has become eligible for the trial, and the assigned treatment will be immediately applied to the infant.

The randomisation procedure is as follows:

- a) Ensure that one machine of each type (FP/Dolphin) is available for use within 10 minutes;
- b) Confirm that the infant meets ALL inclusion criteria;
- c) Confirm that infant does NOT meet ANY exclusion criterion; and
- d) Confirm that informed consent has been received.

If all of the steps are confirmed, the infant's gestational group is identified, to determine the correct stratum, and the next randomisation envelope for that infant will be opened.

4.3. ***Blinding***

Blinding of intervention is not possible, as the machines are visibly different. Some blinding of outcomes assessment will be performed – see item 4.5 Measurement of Outcomes.

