Statistical Analysis Plan

“Randomised trial comparing CPAP machines with reusable vs disposable circuits”

Introduction

1. This document sets out the statistical analysis plan for a randomised trial conducted at Ramaiah Medical College hospital, Bangalore, Karnataka, India, between June 2017 and July 2018 (inclusive). At each point, the plan sets out the text in the original plan and highlights any variations from that plan, as updated on 31 August 2019.
2. **Limitations:** There were two important limitations to the study analysis as envisaged in the protocol:
 - a. The achieved sample size was n=51. This compares to the 80 randomised infants planned for as a feasible target in the setting, despite a 5-month extension to recruitment. The planned sample size was only capable of estimating a major difference (a difference of 0.70 standard deviations between the means) in the primary outcome. The achieved sample size therefore substantially reduces the study power.
 - b. Many of the outcomes, including the primary outcome, were predicated on the assumption that staff would be targeting oxygen saturations of 90-95%, as measured through pulse oximetry (SpO_2); it transpired that this was rarely the case. SpO_2 within the 90-95% target range was achieved in 54 of 224 readings (24.1%) overall, by reading:
 - 14 of 51 (27.5%) of readings at baseline;
 - 9 of 50 (18.0%) of readings at 6 hours;
 - 9 of 49 (18.4%) of readings at 12 hours;
 - 15 of 41 (36.6%) of readings at 24 hours;
 - 4 of 24 (16.7%) of readings at 48 hours; and
 - 3 of 9 (33.3%) of readings at 72 hours.

Exclusion of other outcomes SpO_2 was outside the target readings would have markedly reduced the sample size available, so analysis was continued as planned, including all records, with a note that the analysis may be contaminated. In the case of the primary outcome, for example, the analysis interprets the amount of oxygen required as being reflective of that needed to achieve targeted saturations; when the SpO_2 is above the target range, it is difficult to ascribe meaning to the oxygen level that was provided.

Primary outcome

3. **Descriptive analysis as specified in the protocol:**

Primary and selected secondary outcomes - descriptive: The raw values of the primary outcome (FiO_2) and five secondary outcomes (SpO_2 , respiratory rate, pH, PaO_2 , $PaCO_2$) will be graphed to allow visual comparison of differences at baseline and over time. [Protocol, para 5.2]

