- Kaplan-Meier curve produced to assess treatment failure in the first 72 hours, with difference assessed by log-rank test. Three Dolphin and one Fisher-Paykel failure in first 72 hours; not statistically different by log-rank test, $p=0.30$. Two infants ceased CPAP and were discharged <72 hours (one left against medical advice, the other discharged home), and were excluded from the denominators from the point of discharge. No control for stratification in analysis, as no failures in the older gestational group.

Statistical Analysis Plan

“Randomised trial comparing CPAP machines with reusable vs disposable circuits”

- c. While the difference between groups was not statistically significant in survival analysis, change at in FiO₂ from baseline to 6 hours was preferred as the primary endpoint, given the small sample size. As the distribution was strongly peaked, a non-distributional test (Wilcoxon) was preferred, controlling for stratification (van Elteren's extension).

Secondary outcomes

7. Descriptive analysis as specified in the protocol:

Primary and selected secondary outcomes - descriptive: The raw values of the primary outcome (FiO₂) and five secondary outcomes (SpO₂, respiratory rate, pH, PaO₂, PaCO₂) will be graphed to allow visual comparison of differences at baseline and over time. [Protocol, para 5.2]

8. Descriptive analysis as revised: No change.

9. Analyses as specified in the protocol:

Secondary outcomes: Five of the secondary outcomes (SpO₂, respiratory rate, pH, PaO₂, PaCO₂) will be analysed using the same procedures as for the primary outcome. It is anticipated that the three arterial blood gases (pH, PaO₂, PaCO₂) will not be performed on all infants, particularly infants that recover rapidly; if so, this analysis will be restricted to change from baseline at the 6-hour reading.

Duration of CPAP (hours), for those not failing CPAP treatment, is the only continuous secondary outcome this is expected to be non-normally distributed and will therefore be assessed using Wilcoxon's rank sum test, with stratum-specific contributions aggregated using van Elteren's extension to the Wilcoxon test.^[31]

The remaining secondary outcomes are dichotomous and will be tabulated and compared using stratum-specific relative risks (RRs); the homogeneity of stratum-specific RRs will be assessed using Cochran's Q and the I² tests^[32]. [Protocol, para 5.2]

10. Revisions to planned analysis:

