- a. As with the primary endpoint, change from baseline at the 6-hour reading was adopted as the preferred analysis for SpO₂ (Secondary outcome #2), respiratory rate (Secondary outcome #3), pH, PaO₂, PaCO₂ (all reported as part of Secondary outcome #4) and duration of CPAP (Secondary outcome #8). Due to concerns about non-normality, van Elteren's extension to the Wilcoxon test was used to assess statistical significance, while controlling for stratification by gestational age group. No testing was performed for Secondary outcome #4 (pH, PaO₂, PaCO₂) as there were only five infants who had readings at both baseline and six hours of age.
- b. Dichotomous secondary outcomes were compared using the Cochran-Mantel-Haenszel test, with assessment for homogeneity using the Breslow-Day test. The exceptions to this were:
 - Where there were no events in one stratum (i.e., CPAP failure [Secondary outcome #5], Serious Adverse Event [Secondary outcome #9], Intubation and mechanical ventilation [Secondary outcome #15] and Death [Secondary outcome #17]), Fisher's Exact test was used on the full data; and
 - Where there were no events in either stratum (Damage to the nasal septum [Secondary outcome #10], Damage to the nares [Secondary outcome #11], Pneumothorax

Statistical Analysis Plan

“Randomised trial comparing CPAP machines with reusable vs disposable circuits”

diagnosed by X-Ray [Secondary outcome #12], Intra-ventricular haemorrhage (IVH), intra-cranial haemorrhage (ICH), or periventricular leukomalacia (PVL) as diagnosed by cranial ultrasound scan [Secondary outcome #13], $\text{FiO}_2 \geq 60\%$ to maintain SpO_2 at 90-95% for one hour or more, during CPAP treatment [Secondary outcome #14] and, for infants born at 28+0 to 33+6 weeks' gestation, oxygen dependent at 36 weeks' gestation [Secondary outcome #16]), no statistical test was performed.

Other issues

11. **Multiple comparisons:** The principal control for multiple comparisons was the designation of a single primary endpoint.

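### A gestational stratum with no events is not a valid reason to drop the randomisation strata from the 72-hour log-rank test and four Fisher tests, though the effect is small

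*SAP*

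**What the plan says.** Protocol section 4.2: "Block randomisation with variable block sizes will be used within each of two gestational age strata" (28+0 to 33+6 and 34+0 to 36+6 weeks). The strata were chosen "as the severity of RDS is inversely related to gestation". Protocol section 5.2 carries them into the analysis, with control for stratification in the FiO₂ models and stratum-specific relative risks for dichotomous outcomes.

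The SAP mostly keeps this. Para 6c (the 6-hour FiO₂ change) and para 10a (the continuous secondary outcomes tested) use the van Elteren test. Para 10b uses Cochran-Mantel-Haenszel (CMH) by default for dichotomous outcomes.

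The strata are dropped in two places:
- **Para 6, Kaplan-Meier bullet.** "Three Dolphin and one Fisher-Paykel failure in first 72 hours", with a log-rank p of 0.30. Then: "No control for stratification in analysis, as no failures in the older gestational group".
- **Para 10b.** For CPAP failure (#5), serious adverse events (#9), intubation and ventilation (#15) and death (#17), one stratum had no events, so Fisher's "Exact test was used on the full data".

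No other reason is given in either place.

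**The concern.** A stratum without events does not stop a stratified test from being computed. It carries no information about the arm difference, and the comparison is made where the events are. Pooling instead puts event-free older infants into the denominators, so any uneven allocation between strata enters the result. All four 72-hour failures fell in the younger stratum, which fits the protocol's premise that gestation is prognostic and is a reason to keep the strata.

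At stake are the log-rank p-value and the tests of CPAP failure, serious adverse events, intubation and death. The raw 72-hour split is against the new device. With four events the effect size and its uncertainty matter more than the p-value, and the pooled result does not show whether imbalance in the high-risk stratum raised or lowered it.

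**Working it through.** **Inputs.** From the SAP: 51 infants in total (para 2a); 3 Dolphin v 1 Fisher-Paykel failures within 72 hours, none in the older stratum; log-rank p = 0.30 (para 6). From Protocol section 4.2: block sizes of 4, 6 or 8. Assumed, because the documents give neither: arm sizes of 25/26 or 26/25 (Dolphin/Fisher-Paykel), and 30 younger infants. Event times are not given, so every order of the four events was tried. The two early discharges were not modelled.

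**Formula.** At each event, with a Dolphin and b Fisher-Paykel infants at risk, add a/(a+b) to E and ab/(a+b)² to V. Then χ² = (O−E)²/V on 1 df, with O = 3.

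**Step 1: reproduce the SAP's figure.** Pooled 25/26, Fisher-Paykel failure first: E = 25/51 + 25/50 + 24/49 + 23/48 = 1.959; V = 0.999; χ² = (3 − 1.959)²/0.999 = 1.084; p = 0.298. With that failure last, E = 25/51 + 24/50 + 23/49 + 22/48 = 1.898; V = 0.997; χ² = 1.218; p = 0.270. For 26/25 the range is 0.307 to 0.337. The stated 0.30 is reproduced.

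**Step 2: the empty stratum.** With no event times in the older stratum, both sums are empty: O−E = 0 and V = 0. In an exact stratified test that stratum has only one possible table, with probability 1. As a check with 15/15 younger and 11/10 older infants and one event order:
- Log-rank: stratified p = 0.283, younger stratum alone 0.283, pooled 0.317.
- CMH: p = 0.291 with or without the older stratum; Mantel-Haenszel odds ratio (3×14)/(12×1) = 3.5 both ways.

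**Step 3: size of the effect.**

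| Comparison | Dolphin/FP | Log-rank p, all orders | Relative risk |
|---|---|---|---|
| Pooled | 25/26 | 0.27 to 0.30 | (3/25)/(1/26) = 3.1 |
| Pooled | 26/25 | 0.31 to 0.34 | (3/26)/(1/25) = 2.9 |
| Stratified | 14/16 younger | 0.21 to 0.25 | (3/14)/(1/16) = 3.4 |
| Stratified | 15/15 younger | 0.27 to 0.32 | (3/15)/(1/15) = 3.0 |
| Stratified | 16/14 younger | 0.33 to 0.39 | (3/16)/(1/14) = 2.6 |

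A wider search took 16 to 45 younger infants and imbalance up to 4 in each stratum. Among configurations whose pooled p rounds to 0.30, the stratified p ran from 0.10 to 0.53. Without that restriction the smallest value was 0.053 (16 younger infants split 6/10).

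**Step 4: how much imbalance is plausible.** Imbalance within a stratum cannot exceed half of an unfinished block, so at most 4, and 4 requires the first four places of an unfinished block of 8 to go to one arm. A simulation with the three block sizes equally likely (an assumption), stopped at 30 younger and 21 older infants, gave a younger-stratum imbalance of 4 about 0.3% of the time. Given a 25/26 or 26/25 total, the younger stratum was exactly balanced about 84% of the time.

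**Step 5: Fisher's test.** For 3 v 1, pooled, the probabilities of 0, 1, 2, 3 and 4 Dolphin events are:
- 25/26: 0.060, 0.260, 0.390, 0.239, 0.051. The two-sided p sums the terms no larger than 0.239: 0.239 + 0.051 + 0.060 = 0.35.
- 26/25: 0.051, 0.239, 0.390, 0.260, 0.060. The term for 1 event now counts as well, so p = 1 − 0.390 = 0.61.

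This jump comes from how the two-sided tail is counted, not from stratification. The 3 v 1 split only illustrates the four Fisher outcomes, whose counts the SAP does not give.

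**The case against.** The case against has several parts that stand.

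- **The pooled tests are not invalid.** Under randomisation they remain legitimate, the SAP discloses the departure, and it stratifies the primary endpoint and most other tests. A reader might infer that these comparisons are unsound; the documents do not support that.
- **The log-rank result did not settle the primary endpoint.** Protocol section 5.2 planned it as the check for differential loss, so a reader might infer that a stratified p-value could have changed the primary analysis. SAP para 6c adopts the 6-hour change despite a non-significant log-rank, citing the small sample, so it could not.
- **Large shifts are not realistic.** A reader might take a younger split of 17/13 as the upper extreme. With 25/26 overall that leaves 8/13 older infants, an imbalance of 5, which blocks of 4, 6 or 8 cannot produce. An imbalance of 4 is possible but very unlikely (step 4).
- **A change in Fisher p from 0.35 to about 0.6 is not evidence of a stratification effect.** Switching which arm has 26 infants does the same without stratifying.
- **A stratified log-rank was not explicitly pre-specified.** Protocol section 5.2 names a Kaplan-Meier curve and Cox model for loss, and its stratification sentence follows the FiO₂ models. The Fisher outcomes have the firmer basis, because stratum-specific relative risks were planned for dichotomous outcomes.
- **The SAP does not say that stratifying was impossible.** Its wording could mean that there was nothing to adjust for. On that reading the reason still fails, because the pooled and younger-stratum results differ whenever allocation within strata is uneven.

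None of this rescues the stated reason. It limits the consequence.

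**Conclusion.** The point holds as a minor one. The absence of events in the older stratum does not justify dropping the strata from the para 6 log-rank test or from the para 10b tests of #5, #9, #15 and #17. The stratified versions are defined and reduce to the younger stratum; only homogeneity cannot be assessed.

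For 72-hour failure the realistic effect is a modest shift. If the younger stratum is balanced, the pooled and stratified results nearly coincide; with an imbalance of 2 among 30, the shift is the one shown in the table. No configuration tried fell below 0.05. These figures rest on assumed arm sizes, stratum sizes and event orders. The effect on the four Fisher outcomes cannot be sized from the documents. The SAP gives no relative risk for any of these outcomes, so the relative risks here are illustrations and not corrections of a reported value.

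**What to change.** - SAP para 6: stratify the log-rank test by gestational group.
- SAP para 10b: for #5, #9, #15 and #17, replace Fisher's test on pooled data with an exact test stratified by gestational group, and note that homogeneity cannot be assessed.
- Both paragraphs: remove the absence of events in one stratum as the reason for not stratifying.
- Report events and denominators by arm and stratum for these outcomes, so that a reader can see the younger-stratum comparison directly.

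The cost is a few lines of SAP wording and a re-run with options in existing SAS procedures. No new data are needed.

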Primary outcome: With longitudinal measurement, the interpretation of later results can be impacted by differential losses before 72 hours (death or intubation and ventilation). Analysis will therefore commence with a Kaplan-Meier curve comparing 'loss' (death or intubation and ventilation), and an associated Cox regression model to compare the rate of loss in the two treatment arms. The results of this survival analysis will provide the context within which the longitudinal results will be interpreted. If there are differential losses over time, the least affected time point will be 6 hours after treatment commencement, and this time point will be promoted to being the primary outcome. If losses over time are not differential, the planned analysis is described below.

The preferred omnibus analysis is a longitudinal mixed effects model (using PROC MIXED in SAS 9.4), controlling for baseline through a random 'intercept', in line with international recommendations for controls on baseline.^[30] Individual analyses at each time point (6, 12, 24, 48, and 72 hours) will be by multiple regression, again adjusting for baseline as a covariate.^[30] If multiple regression model requirements for normality and homoscedasticity are not met, analysis will be by t-test which is known to be robust to violations of the normality assumption, and will be based on the change in variable from baseline value, providing some control for different baselines, but without the additional control offered by multivariate analysis.

Where performed, multivariate analysis will control for stratification; if univariate analysis is used, separate stratum-specific sub-analysis will be undertaken, and a stratified t-test will be performed. Additional covariates will be adjusted for in multivariate analysis, if the baseline comparison shows substantial group difference in significant prognostic factors (e.g., onset of labour is associated with the stimulation of surfactant production, so analysis will control for mode of delivery if there is a clinically relevant mal-distribution).

Secondary outcomes: Five of the secondary outcomes (SpO_2 , respiratory rate, pH, PaO_2 , PaCO_2) will be analysed using the same procedures as for the primary outcome. It is anticipated that the three arterial blood gases (pH, PaO_2 , PaCO_2) will not be performed on all infants, particularly infants that recover rapidly; if so, this analysis will be restricted to change from baseline at the 6-hour reading.

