Duration of CPAP (hours), for those not failing CPAP treatment, is the only continuous secondary outcome this is expected to be non-normally distributed and will therefore be assessed using Wilcoxon's rank sum test, with stratum-specific contributions aggregated using Elteren's extension to the Wilcoxon test.^[31]

The remaining secondary outcomes are dichotomous and will be tabulated and compared using stratum-specific relative risks (RRs); the homogeneity of stratum-specific RRs will be assessed using Cochran's Q and the I^2 tests^[32].

Software: All analysis will be conducted in SAS/STAT® 9.4, except for the calculation of stratum-specific and pooled relative risks, which will be performed in RevMan 5.3.^[33]

6. **Clinical protocol:**

6.1. **Interventions**

This study compares routine CPAP care on existing machines with CPAP care on a new machine that uses a re-usable humidifier and tube set.

Routine CPAP care will be on a Fisher & Paykel [FP] CPAP machine which includes separate oxygen and medical air intakes, a FP blender, and a disposable FP humidification chamber and tube set including a heater wire (Fisher & Paykel Healthcare Ltd, Auckland, New Zealand; hereafter referred to as FP CPAP). The new machine (hereafter referred to as the 'Dolphin CPAP') includes an oxygen intake, an on-board air compressor, built in Massimo pulse oximeter (not used in this study – see para 4.5 above), and an autoclavable humidifier and tube set.

6.2. **Treatment protocol features that are common to both arms**

The following systems will be common to both groups regardless of treatment allocation:

- Baby interface: An identical FP infant interface will be used for both groups of babies; this may require the creation of a special adaptor to permit use of the FP interface with the Dolphin CPAP tube set if the FP interfaces for non-FP connectors is not identical to the FP interface for FP tube sets;
- Pulse oximetry: The FP CPAP does not include built-in pulse oximetry, while the Dolphin CPAP does. To ensure consistency in measurement of pulse oximetry, Ramaiah Medical College will use a single pulse oximeter (built into the Mindray MEC 3000), for monitoring SpO₂ on all infants regardless of the treatment allocation. This ensures that any measurement error in SpO₂ will be non-differential.

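### SAP 6c makes 6-hour FiO2 change primary, tested by van Elteren, on grounds that Protocol 5.2 does not give, and does not say whether FiO2 by arm had been seen

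*SAP*

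**What the plan says.** Protocol 5.2, Primary outcome (reproduced in SAP para 5), starts from a comparison of losses between arms, where a loss is death or intubation and ventilation. If losses are differential, the 6-hour reading is taken as least affected and "this time point will be promoted to being the primary outcome". The alternative branch is explicit: "If losses over time are not differential, the planned analysis is described below". That branch prefers a longitudinal mixed model, with multiple regression adjusted for baseline at each of 6, 12, 24, 48 and 72 hours. If normality or homoscedasticity fails, the fallback is a t-test on change from baseline, for which "separate stratum-specific sub-analysis will be undertaken, and a stratified t-test will be performed". The van Elteren test appears in the protocol only for duration of CPAP, which "is the only continuous secondary outcome this is expected to be non-normally distributed".

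SAP para 6 reports the loss comparison as "Three Dolphin and one Fisher-Paykel failure in first 72 hours; not statistically different by log-rank test", with p=0.30. Para 6c begins "While the difference between groups was not statistically significant in survival analysis" and goes on to say that the FiO2 change "from baseline to 6 hours was preferred as the primary endpoint, given the small sample size". On the test it says: "As the distribution was strongly peaked, a non-distributional test (Wilcoxon) was preferred", with van Elteren's extension for the gestational strata. Para 11 names the single primary endpoint as the main protection against multiple comparisons, leaves secondary endpoints unadjusted, and reads any significant secondary result in the context of the primary one. Para 1 dates the update 31 August 2019, for a trial run from June 2017 to July 2018.

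**The concern.** The reason given for the time point, small sample size, is not a condition in the promotion rule. The reason given for the test, a peaked distribution, is close to the problem the protocol foresaw and answered with a different test. Both decisions appear in a document updated after the trial ended, which already cites failures by arm and the shape of the distribution.

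Seeing the losses and the distribution is not a fault in itself, because the protocol's rules depend on them. What matters is FiO2 by arm. A single primary endpoint protects the 5% level only if the time point and test were chosen without reference to that comparison, and the SAP does not state this. The SAP also does not say whether the mixed model was run. The protocol's preferred analysis may therefore go unreported in a trial that reached 51 of 80 infants.

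**Working it through.** **1. The rule and the decision, side by side.**
- Trigger for 6 hours in Protocol 5.2: differential losses. Reason in SAP 6c: small sample size.
- Where the protocol wanted incomplete readings to restrict analysis to 6 hours, it said so, but only for the three arterial blood gas measures, not for FiO2.
- Fallback for failed regression assumptions in Protocol 5.2: stratified t-test on change. Test in SAP 6c: van Elteren. A peaked distribution is also not quite the protocol's condition, which concerns the regression model's normality and homoscedasticity.

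**2. What the losses can show.** Inputs: 3 v 1 failures (SAP para 6); equal arms assumed.
- Reproducing the SAP's p-value: z = (3 - 2)/sqrt(4 x 0.25) = 1, p = 0.32, consistent with the reported 0.30.
- Hazard ratio about 3/1 = 3. SE of the log hazard ratio = sqrt(1/3 + 1/1) = 1.155. 95% CI = exp(ln 3 ± 1.96 x 1.155) = about 0.3 to 29.
- The losses are therefore not shown to be differential, and not shown to be balanced.

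**3. Information set aside by using 6 hours only.** Inputs: SpO2 reading counts in SAP para 2b, used as a proxy for FiO2: 50, 49, 41, 24 and 9 at 6, 12, 24, 48 and 72 h. Assumptions: monotone dropout and a constant treatment effect.
- Total 50 + 49 + 41 + 24 + 9 = 173. The 6-hour analysis uses 50/173 = 29%. Readings at 6-24 h are 140/173 = 81%.
- Monotone dropout gives 1, 8, 17, 15 and 9 infants with 1, 2, 3, 4 and 5 readings.
- With equal correlation c, an infant with k readings contributes k/[1 + (k - 1)c], relative to one reading.
- Change scores under a random intercept have c = 0.5. Sum = 1 + 8(1.333) + 17(1.5) + 15(1.6) + 9(1.667) = 76.17. Divided by 50 this is 1.523. SE ratio = 1/sqrt(1.523) = 0.810, so 19% smaller.
- Baseline-adjusted, c = rho/(1 + rho). For rho = 0.7, 0.5, 0.3 the information ratio is 1.683, 1.858, 2.155, so the SE is 23%, 27%, 32% smaller.
- If correlation instead decays exponentially with time (6-hour correlation 0.7, 0.5, 0.3), the SE is 3%, 7%, 11% smaller for change scores and 17%, 30%, 39% smaller baseline-adjusted.
- Range over all scenarios: 3% to 39%.

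**4. Type I error, by what the choice depended on.**
- Nothing to do with FiO2 by arm: 5%.
- Only the test at 6 hours chosen on the result (stratified t-test or van Elteren): about 6-7%. This comes from simulation under the null with 20,000 runs per setting, 50 infants in two strata of 25, and normal or Laplace data.
- Mixed model or one 6-hour test, whichever is better: the correlation between the two statistics equals the SE ratio. The equal-correlation cases in step 3 then give 7.7% (change scores) to 8.4% (baseline-adjusted).
- Same choice with van Elteren as the 6-hour test, simulated with the settings above and the mixed model approximated by baseline-adjusted weighted infant means: 8.3-9.4%.
- Best of mixed model, stratified t-test and van Elteren, simulated the same way: 9.2-10.4%. Each test alone gave 4.7-5.4%.

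**The case against.** The best defence is that 6c is a concession. Its sentence can be read as saying that, with so few infants, a non-significant log-rank test is not reassuring, so the protocol's own safer time point was used. SAP para 2a has already said that power is substantially reduced, and the protocol sets no threshold for differential. This largely stands: on that reading the 6-hour time point is consistent with the protocol. But 6c does not say that losses were treated as differential, and a reader has to supply the argument.

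The change is also disclosed. Para 5 reproduces the protocol text, para 6 lists the revision, para 1 dates it, and para 11 calls the study exploratory and undertakes to acknowledge the risks of multiple comparisons. That stands too. Disclosure leaves two gaps: what was known of FiO2 by arm, and whether the mixed model will be reported.

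Van Elteren is a reasonable test. It respects the stratification and is the protocol's method for the one outcome expected to be non-normal. The objection here is to an unlabelled swap, not to the test's validity.

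The mixed model has weaknesses. It is a normal-theory model applied to a peaked distribution. Readings fall from 50 to 9 by 72 hours, far more than four failures explain, so the later infants are a selected group and a constant effect may be optimistic. These are reasons to report it with care, not to omit it.

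A reader might infer that the endpoint was picked because of its result. The documents do not support that: 6 hours was a planned time point and the rule's named alternative, and nothing shows that FiO2 by arm guided the choice.

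**Conclusion.** The point holds as a departure from the written rule with an incomplete explanation, and should be fixed. The stated reason for 6 hours is not the protocol's trigger, the test is not the protocol's fallback, and para 11 relies on the resulting endpoint without saying how it was reached.

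Two stronger conclusions should not be drawn. Losses have not been shown to be balanced, so 6 hours is not clearly the wrong time point: the interval of about 0.3 to 29 leaves that open. Nor is the trial's type I error 8-10%. That figure applies only if both time point and test were selected on FiO2 by arm. It is about 6-7% if only the test was, and 5% if neither was.

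The 3-39% gain in precision is illustrative and rests on the SpO2 proxy, monotone dropout and constant effect. The textual finding needs none of these figures.

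**What to change.** 1. In SAP 6c, report the protocol's mixed model over 6-72 h, with baseline and gestational stratum, as the protocol-specified primary analysis. Note the sparse readings at 48 h and 72 h (24 and 9 by SpO2 counts), and check residuals because the distribution is peaked.
2. Report the 6-hour van Elteren result beside the protocol's own 6-hour analyses: baseline-adjusted regression and, if its assumptions fail, the stratified t-test. Label it a departure from Protocol 5.2 and state whether FiO2 by arm had been seen when it was chosen.
3. Alternatively, if the sponsor treats 3 v 1 as differential because so few events cannot exclude it, say so in 6c in place of the sample-size reason. Give the hazard ratio with its interval; Protocol 5.2 already planned a Cox model. The 6-hour time point then follows the protocol, and only the change of test needs the label.
4. In para 11, state that FiO2 was named in advance and that the test (and, unless option 3 is adopted, the 6-hour time point) was adopted in the revision.

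The cost is SAP wording and a few analyses the protocol already specified, on data already held. The downside is a little more analysis and a weaker label on the 6-hour result.
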